rTMS administration: The rTMS operator will be fully trained and qualified to administer the procedure according to current safety practices and standards of care. Co-Is [name] and [name] have full rTMS training and, together with physician Co-Is also trained in rTMS, closely monitor the rTMS operator for adherence to safety protocols and rTMS administration for this proposal. Additionally, PI [name] will obtain full rTMS training and be available as an additional monitor and resource to the rTMS operator. The protocol employs all current established and standard rTMS treatment safety and monitoring for adverse events guidelines. The rTMS operator will monitor all participants for ear protection, coil placement, and seizure activity during all sessions.

All participants will be required to have abstained from alcohol or non-prescribed medication for 7 consecutive days prior to the first rTMS session. Prior to the first rTMS session, participants will be administered the CIWA- Ar and must score <8 (scores >8 are indicative of potential autonomic instability); participants with a score >8 will immediately be escorted to VAPAHCS ATS or further evaluation. Participants will be randomly screened x6 for alcohol (breath alcohol) and substance use (urine toxicology) prior to rTMS sessions during the 2-week treatment phase. If a participant tests positive or reports any alcohol or substance use during the 2-week rTMS treatment period, they will be immediately withdrawn from the study. Additionally, participants will be given the C-SSRS prior to each rTMS session to assess for current suicide risk. Although patients in the VAPAHCS are regularly screened for alcohol and substance use and suicide risk while in treatment, we will conduct random alcohol/substance screening and pre-rTMS session suicide risk assessment to ensure participant welfare.

Should a headache or site of stimulation discomfort occur, these symptoms usually readily respond to acetaminophen or ibuprofen. Any reported painfulness typically improves over time or completely remits. If dental pain

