occurs, study staff may be able to move the rTMS coil position or provide a bite block to reduce or eliminate this pain. To protect against possible hearing damage, participants will wear ear protection during rTMS sessions. This should greatly reduce the possibility of hearing loss. Hearing acuity testing pre-and-post rTMS is no longer a standard practice, given the remote likelihood of rTMS-related hearing loss.

Screening, Baseline and Treatment Phase: In the unlikely event that a seizure does occur, participants will be closely monitored and treated for any medical or psychological consequences. rTMS sessions will be conducted at the VAPAHCS MIRECC, which fully equipped to safely handle a seizure. If at any point during study participation, a participant has a seizure, the participant will be withdrawn from the study immediately although they will still be followed for protocol assessments. All seizures will be considered serious adverse events (SAE) and as such, will be reported to the study PI. We will immediately suspend enrollment if any of the participants experience a seizure during study participation and request that the Data Monitoring Safety Board (DMSB) evaluate the SAE data, to determine if enrollment of new participants should be resumed without protocol changes, if protocol modifications should be made before resuming enrollment, or if the study should be terminated. We recognize that study termination or modification based on SAEs, such as seizures, ultimately rests with the DMSB and the study PI. If a participant expresses suicidal ideation/intent and is determined to be a risk to self, a clinical evaluation will be immediately conducted by the PI (a licensed clinical psychologist), Co-Is (two licensed clinical psychologists and a board-certified psychiatrist), or by the participant's individual mental health provider, and/or a mental health emergency clinician. The participant will remain with qualified study personnel or a MIRECC clinician until the evaluation has been completed and a decision made about disposition in conjunction with the Chief of Mental Health Outpatient Clinic or the emergency mental health clinician.

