An Adverse Event (AE) is defined by the ICH for Clinical Safety Data as any untoward physical or psychological occurrence in a human subject participating in research. The AE does not necessarily have to have a causal relationship with the pharmacological product, study intervention, or assessment. An AE can, therefore, be any unfavorable or unintended sign including an abnormal laboratory finding, symptom or disease associated with the use of a medicinal investigational product.

An Adverse Device Effect (ADE) is defined by 21 CFR 812.3s as any adverse effect/event caused by or associated with the use of a device.

Reporting: In this study, all ADEs and AEs that occur during the acute treatment and follow-up phases will be collected and followed until resolution or the individual's participation in the study ends. All events will be recorded on the appropriate case report form. "Relatedness" involves an assessment of the degree of causality between the study intervention and the event. PIs will be asked to provide an assessment of relatedness. The assessment provided by the PI is part of the information used by the sponsor to determine if the adverse event or effect presents a participant safety concern. An ADE is deemed to be

associated with the use of the study device if there is a reasonable possibility that the experience may have been caused by the device or by participation in the trial. Thus, all adverse events or effects with a reasonable causal relationship to the rTMS treatment should be considered related. A definite relationship does not need to be established. The following levels of relatedness will be used in this study:

- Not attributed to TMS treatment
- Possibly attributed to the TMS treatment
- Attributed to the TMS treatment

Serious Adverse Events (SAEs) and Unanticipated Adverse Device Effects (UADEs)

Definitions:

Serious Adverse Events (SAEs) are a subset of adverse events and are defined by the ICH for Clinical Safety Data Management as any untoward medical occurrence that:

- Results in death
- Is life-threatening
- Requires inpatient hospitalization or prolongation of existing hospitalization
- Results in persistent or significant disability or incapacity
- Is a congenital anomaly/birth defect or
- Any other condition that, based upon medical judgment, may jeopardize the subject and require medical or surgical treatment to prevent one of the above outcomes.

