An Unanticipated Adverse Device Effect UADE is defined as any serious adverse effect on health or safety or any life-threatening problem or death caused by, or associated with, a device, if that effect, problem, or death was not previously identified in nature, severity, or degree of incidence in the investigational plan or application, or any other unanticipated serious problem associated with a device that relates to the rights, safety or welfare of participants. For this study an UADE is considered a category of SAE, which will be reported on the same form.

Collection and Recording: For this study, all SAEs and UADEs will be recorded on the SAE form, regardless of cause. The PI will be asked to determine whether the serious adverse event is related to:

- rTMS device
- rTMS treatment
- Medications used to treat AUD and/or co-occurring conditions

Collecting and recording SAEs/UADEs will begin at randomization and will continue throughout the follow-up phase. For a participant who ends study participation prior to the study's completion date, unresolved SAEs will be monitored and reported for 30 days after the End of Study date for that participant. In addition, the investigator must collect all SAEs reported to them for a period of 30 days after the study's completion.

Expedited Reporting of Serious Adverse Events SAEs and Unanticipated Adverse Device Effects UADEs: Study personnel will be responsible for initially evaluating all serious adverse events for participant safety concerns and will confer with the PI as required during this evaluation process. After being reviewed by the PI, any event deemed to be related, serious and unexpected will be reported to study investigators.

Expedited Reporting by the Sponsor to the FDA: PI will review the SAE report to assess completeness of documentation and to determine whether the SAE requires expedited reporting to the FDA. Specifically, if an event meets the criteria for unexpectedness (i.e., not previously reported and seriousness) it will be reported as required by regulation to the FDA within 10 working days for UADEs and within 7 calendar days for unexpected SAEs. Safety Reports of the sponsor receiving the report as required by regulation.

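### Participants who leave early get no follow-up of open non-serious adverse events and no active search for new serious ones, and the protocol's exit terms do not agree

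*Protocol*

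**What the plan says.** The rules sit in four places in the Protocol.

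- **Adverse Events and Adverse Device Effects, Reporting.** All AEs and ADEs in the treatment and follow-up phases "will be collected and followed until resolution or the individual's participation in the study ends".
- **SAEs and UADEs, Collection and Recording.** The general rule is "Collecting and recording SAEs/UADEs will begin at randomization and will continue throughout the follow-up phase". For a participant who leaves before the study's completion date, "unresolved SAEs will be monitored and reported for 30 days after the End of Study date for that participant". The closing sentence adds that "the investigator must collect all SAEs reported to them for a period of 30 days after the study's completion". The definition just above states: "For this study an UADE is considered a category of SAE".
- **Procedures to Minimize Risk.** Under rTMS administration, participants who test positive for or report alcohol or substance use during the two treatment weeks are dealt with in one clause: "they will be immediately withdrawn from the study". Under Screening, Baseline and Treatment Phase, a seizure is classed as an SAE and "the participant will be withdrawn from the study immediately although they will still be followed for protocol assessments".
- **Study Conclusion.** The experiment ends for a subject at normal termination or on the subject's own decision to withdraw. The next sentence says that participants will be asked to do the brief follow-up assessments, without saying whether people who have left are included.

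**The concern.** Safety observation should not be shortest in the people most likely to have had trouble with the intervention. Here, someone who tolerates dTMS and stays abstinent is observed for months. Someone who leaves because of a non-serious device effect, or who is withdrawn for drinking, may be observed only up to the day of exit. What can be lost is the duration and outcome of a non-serious effect open at that moment, and any serious event that begins shortly afterwards and that nobody reports.

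The Benefits section intends this pilot to show whether the treatment is workable and tolerable enough to justify a larger study. With 10 participants, incomplete safety information on even one early leaver is a visible share of the evidence.

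**Working it through.** The plan gives no figure to reproduce, so the check compares the rules by type of event, for a participant who leaves the study early.

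1. **Non-serious AE or ADE open at exit.** The Reporting paragraph stops when participation ends, and the SAE paragraph does not apply. Follow-up after exit: 0 days.
2. **SAE or UADE unresolved at exit.** A UADE counts as an SAE, so both fall under the early-leaver sentence. Follow-up after exit: 30 days.
3. **Seizure leading to withdrawal.** Always an SAE, and assessments continue. The planned contacts are at 2, 4 and 6 months.
4. **New SAE that first occurs after exit.** The early-leaver sentence covers only unresolved SAEs, so it does not reach this event. Two other sentences might.
   - The general rule runs through the follow-up phase, but the text does not say whether a withdrawn person is still in that phase.
   - The closing sentence depends on the meaning of *the study's completion*, which is undefined. If it means the end of the trial (probable duration 2.5 years) and the duty runs up to 30 days past it, a reported event is covered. If the window opens only at that date, an event one week after an early exit falls before it. If it means the participant's own completion, the text does not say whether an early leaver has one.
   - On every reading collection is passive: it covers SAEs reported to the investigator.
5. **Withdrawal for alcohol or substance use.** The clause carries no statement on continued assessment, unlike the seizure clause. The same word, withdrawn, thus has two apparent consequences.

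**Illustration of size.** Inputs: treatment over two weeks (14 days); follow-up of 6 months, taken as 6 × 30 = 180 days; 10 participants.

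- Completer: 14 + 180 = 194 days of planned collection.
- Exit on day 2: 2/194 = 1.0%. Exit on day 14: 14/194 = 7.2%.
- With 30 days added after exit: (2 + 30)/194 = 16.5% and (14 + 30)/194 = 22.7%.
- One early leaver: 1/10 = 10% of the sample.

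The exit days are chosen, not estimated, because the Protocol gives no withdrawal rate. A completer's 194 days also contain only three planned brief contacts after the post-treatment visit, so the contrast in actual ascertainment is smaller than these ratios suggest.

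**The case against.** The strongest reply is that this is a coherent tiered rule: ordinary events are followed to the end of participation, serious ones for 30 days more. Most of the expected device effects are described as brief, and an event that makes someone leave is still recorded with a relatedness assessment. Only its later course may be lost. All of this stands, and it limits the point.

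A reader might infer more than the text supports, in three ways.

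- *Any device effect that makes someone stop goes unfollowed.* Not so. Serious effects unresolved at exit have 30 days and seizure cases keep their assessments. The limit is also triggered by the end of participation, not of stimulation: nothing says that a person who stops sessions for headache or scalp pain has left the study. Nor must an effect that leads to stopping still be open at exit.
- *A new SAE after withdrawal falls under no rule at all.* Not so. The closing sentence on SAE collection is limited neither to unresolved events nor to completers. What is missing is active ascertainment and a clear window.
- *The safety results will be biased in favour of dTMS by a known amount.* The documents do not show this. They give no withdrawal rate, and the Benefits section does not say that tolerability will be judged on event duration. A discontinuation would itself count against acceptability.

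The sentence in Study Conclusion on brief assessments does not close the gap. It does not say that it applies to leavers, and the Monthly Follow-ups section describes those contacts as measuring drinking, substance use and craving.

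**Conclusion.** The concern holds in a limited form. For early leavers, non-serious AEs/ADEs open at exit have no further follow-up, and no one is required to look for new SAEs. The alcohol and seizure withdrawal clauses differ on continued assessment, and *withdrawn*, *End of Study date* and *the study's completion* are not used in a way that settles who is still observed. Length of safety observation therefore depends partly on tolerability and abstinence.

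The number of people affected cannot be stated from the Protocol; the 1% figure describes one chosen exit day. The conclusion assumes that an immediate withdrawal from the study ends participation unless the text says otherwise, as it does for seizures. If the sponsor intends continued assessment for everyone withdrawn, the gap narrows to wording, but that wording is still needed. This is an inexpensive improvement to safety data collection, not a defect that undermines the study.

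**What to change.** 1. Keep the present limit on AE/ADE follow-up for completers. Do not replace it with a uniform cap of 30 days after the last session, which would cut up to 180 − 30 = 150 days, about 5 months, of follow-up for an unresolved event in a completer.
2. For early leavers, add to the Reporting and the Collection and Recording paragraphs that AEs/ADEs open at exit are followed, and all SAEs including new ones are collected, for 30 days after that participant's End of Study date. Include one active contact at about day 30 unless consent to contact is withdrawn. The 30 days is the Protocol's own interval for unresolved SAEs.
3. Define *withdrawn*, *End of Study date* and *the study's completion* once, and reconcile rTMS administration, the seizure paragraph, Reporting, Collection and Recording, and Study Conclusion with those definitions. In particular, state for each kind of withdrawal whether data collection continues.

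This changes data collection only, not who is withdrawn or how anyone is treated. The cost is a short amendment and one telephone call per early leaver, so at most 10 calls.

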2. DEVICES USED IN THE STUDY

Investigational Devices (Including Commercial Devices Used Off-Label)

Investigational Device 1	
Name:	3T UHP
Description:	GE 3T Ultra High Performance (UHP) MRI scanner GE Healthcare
Significant Risk? (Y/N)	No
Rationale for Non-Significant Risk	The GE 3T Ultra High Performance (UHP) MRI scanner is an upgrade of an FDA-approved 3T MR750 scanner but is not itself FDA approved. The UHP scanner utilizes components from GE's 3T Signa Premier scanner (an FDA approved system) including gradient drivers, power supply, transmit and receive system, but uses a higher-performance gradient coil. The scanner has been tested by GE according to UL60601-1 and for compliance with IEC60601-2-33 (ed 3.1), meeting limits and guidelines for peripheral nerve stimulation, patient thermal, SAR limit, acoustic noise, flammability rating UL94-5VA for safety covers, hydrostatic pressure, electrical hazards, dielectric strength and pinch point. MRI research scans also frequently require specialized research software, but this will conform to FDA guidelines for MR safety related to heating (SAR), peripheral nerve stimulation (dB/dt), and acoustic noise. As a result, the 3T UHP system is considered a non-significant risk investigational device and is subject to 21 CFR 812 investigational device (IDE) regulations as well as 21 CFR 50 and 56. The MRI scans in this study using the UHP scanner will utilize operational parameters within FDA guidelines for Nonsignificant Risk thus an Investigational Device Exemption (IDE) from FDA should not be necessary. In addition to the GE receive coil components that are included with the UHP system, there are some non-GE coils. These devices are legally marketed components, used in accordance with their labelling, and are of non-significant risk. They include 32 channel and 16 channel receive-only brain RF coil arrays, manufactured by Nova Medical, Inc.
Investigational Device 2	
Name:	BrainsWay Deep TMS H7 coil
Description:	Deep TMS is FDA-cleared for other impulse control disorders and specifically the BrainsWay H7 Deep TMS coil was FDA-approved for OCD in September 2017 (DEN170078)101.
Significant Risk? (Y/N)	No
Rationale for Non-Significant Risk	Deep TMS is FDA-cleared for other impulse control disorders and specifically the BrainsWay H7 Deep TMS coil was FDA-approved for OCD in September 2017 (DEN170078)101. Review of the clinical summaries

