Magnetic Resonance (MR)Studies: Participants will be informed of risks, using the text provided and required by Stanford University's Institutional Review Board the VA. Our Research Assistants (RA) have been trained by the PI, Co-Is carefully pre-screen each participant for MRI safety before the MRI appointment. RAs also have been certified to independently operate the CNI magnetic resonance scanner by qualified CNI personnel. Minimal risks are associated with MR scanning and 3T MR scanners are now routinely used in clinical practice. Study participants who have metal implants, cardiac pacemakers, metal fragments or a known tendency for claustrophobia will not be admitted to the study. Study participants will be scanned with a metal detector before entering the 3T scanner room, and all metal objects will be removed. There is a remote possibility that the magnet will attract a metal object, producing physical injury. To make certain such event do not occur, the door to the magnet room is closed and there is a metal detector outside the door to ensure no ferromagnetic metals are allowed into the scanner. One theoretical hazard of the experiments is heating of the body due to radio waves, but the machine has several safety devices to prevent such an occurrence. There is also a slight risk of nerve stimulation during a portion of the procedure. While there are safety devices that prevent such events, this can occur in rare cases. To reduce this risk, volunteers will be instructed to avoid skin-to-skin contact between their extremities, such as clasping their bare hands or crossing their bare feet. In any case, such sensation is temporary and harmless. Fatigue, boredom, feelings of claustrophobia, or discomfort due to loud banging sounds of gradient coils may accompany the MR procedures. Earplugs and supplied MR-safe headphones will be used during MR scanning. A communication system is set up inside each scanner so that study participants can contact the researchers at any time, and will be immediately removed from the scanner upon request. In case of adverse effects, medical intervention can be provided by Stanford Emergency Department staff. Study physicians will be available in the case of an adverse event to debrief with the participant.

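### Two investigational devices are named, but no adverse-event relatedness level and no SAE attribution item can record the MRI scanner as the cause

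*Protocol*

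**What the plan says.** The protocol's section on devices lists two investigational devices. The first is the MRI scanner: "the 3T UHP system is considered a non-significant risk investigational device and is subject to 21 CFR 812 investigational device (IDE) regulations". The second is the "BrainsWay Deep TMS H7 coil". The Procedure Risks section adds that some image-acquisition software will also be investigational.

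The definitions under Adverse Events and Adverse Device Effects, and those under Serious Adverse Events and Unanticipated Adverse Device Effects, are device-neutral: an ADE or UADE may arise from any device.

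The coding rules are not device-neutral. Under Reporting, one sentence counts an ADE as associated with the study device where the device, or taking part in the trial, may reasonably have caused it. The next sentence reads: "Thus, all adverse events or effects with a reasonable causal relationship to the rTMS treatment should be considered related". A three-level scale follows. Its first two levels are "Not attributed to TMS treatment" and "Possibly attributed to the TMS treatment", and the third is attribution to TMS treatment outright.

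For serious events, Collection and Recording says "The PI will be asked to determine whether the serious adverse event is related to" one of three things: the rTMS device, the rTMS treatment, or medications for AUD or co-occurring conditions.

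The risk section on MR studies describes scanner harms, including: "There is also a slight risk of nerve stimulation during a portion of the procedure". It also mentions heating, a metal object drawn to the magnet, and claustrophobia or discomfort.

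**The concern.** The definitions extend to both investigational devices, but the categories used to apply them cover only one. An investigator who believes the scanner caused an event, and TMS did not, has one honest choice on the AE scale: "Not attributed to TMS treatment". An event unrelated to anything in the study gets the same code.

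Three things are at stake:

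- Scanner effects cannot be separated from unrelated events in the safety tabulations.
- The protocol says the relatedness assessment informs the sponsor's judgement on participant safety. For scanner events that input would be uninformative.
- Reporting to study investigators is limited to events judged related, serious and unexpected. Whether a scanner event counts as related depends on which of two adjacent sentences is followed.

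**Working it through.** The protocol gives no figure to reproduce. The check sets the device list and definitions beside the coding categories and reporting routes.

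**Category count**

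- Investigational devices listed: 2 (scanner, H7 coil).
- AE relatedness levels: 3, all naming TMS.
- SAE attribution items: 3, of which 2 name rTMS and 1 names medications.
- Total: 3 + 3 = 6 categories. TMS is named in 3 + 2 = 5 and medications in 1. The scanner is named in 0 of 6. Neither list, as printed, has an item for study procedures or for other causes.

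**The two adjacent sentences, applied to an event caused by the scanner alone**

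- First sentence (the device, or participation in the trial): a research scan is part of taking part, so the event counts as associated.
- Second sentence and the scale (rTMS treatment): nothing makes the event related, and the only code that fits is the lowest.

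The second sentence is written as a consequence of the first, yet it is narrower. The same event can be called associated or not attributed, depending on where the reader stops.

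**Which routes depend on the code**

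- Recording of SAEs and UADEs: no. They go on the SAE form whatever the cause.
- Recording of AEs and ADEs: no. All within the stated window are collected.
- Expedited report to the FDA: no. The stated criterion is unexpectedness and seriousness.
- SAE report within 24 hours and unanticipated-problem report within 5 days (Data Safety Monitoring Plan): no.
- Report to study investigators: yes. The event must be judged related as well as serious and unexpected.
- Attribution in the AE and SAE tabulations: yes, to the extent that they use the coded fields.

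**Exposure**

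- Planned enrolment is 10, with a baseline and a post-treatment scan each: 10 × 2 = 20 scans at most. Early withdrawal would reduce this.
- Baseline scans: 10 × 1 = 10 of the 20.

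**Collection windows**

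- AE/ADE collection names acute treatment and follow-up. The baseline assessment is not named.
- SAE/UADE collection starts at randomization. The design section describes one group of 10 receiving deep TMS, so that starting point has no clear date.
- The post-treatment scan comes within days of the last session. By calendar it falls in the period after treatment, and I read it as covered. The baseline scan is not clearly covered by either window.

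**The case against.** The strongest reply is that the scale suits the study. Relatedness is defined against the study intervention, which is dTMS, and the Procedure Risks section says the research does not evaluate the scanner's safety or efficacy. The scanner is rated non-significant risk. Nerve stimulation is called temporary and harmless, heating is called theoretical, and no serious event is reported from scanning at that centre. Harms already described in the protocol would usually not be unexpected, whatever their code. The study has 10 participants and the PI reviews SAEs personally. The forms themselves are not shown and may have a free-text or other-cause field.

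Much of this limits the consequence, but it does not remove the mismatch. The H7 coil carries the same non-significant-risk rating and its causality is rated, so risk class does not explain the difference. The research aim does not narrow the ADE and UADE definitions, which make no exception for a measurement device.

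A reader might go further and infer that a scanner harm could never surface as a device effect, or that a serious one would fail expedited reporting. The protocol does not support this. Its definitions allow a scanner event to be classed as an ADE or UADE, recording of serious events does not depend on cause, and neither the FDA criterion nor the 24-hour rule uses the TMS code. Nor does the second sentence say that only rTMS-linked events are related; it names one sufficient condition. It would also be inaccurate to say that causality is rated against TMS alone, because SAEs are also rated against medications.

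**Conclusion.** The point holds as a conflict between the protocol's definitions and its coding categories. What is missing is a coded attribution to the scanner, together with a consistent answer at the one reporting step that requires a related event. Capture of the event and its regulatory reporting are not lost.

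The size is 0 of 6 categories for one of two investigational devices, over at most 20 scans. That is a count of exposures; the protocol gives no rate from which to predict events, and its own description suggests few. For the 10 baseline scans the collection window is an earlier obstacle than the code, and extra categories alone would not remove it.

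The conclusion assumes that the forms follow the lists as printed. If they carry an other-cause field, the practical loss is smaller, but the two adjacent sentences still need reconciling. Given the small expected consequence and the very low cost, this is a change the sponsor should make, though not one that threatens the study.

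**What to change.** - Under Reporting, apply the existing three-level scale separately to (a) dTMS with the H7 coil, (b) the 3T UHP scanner with its investigational sequences, and (c) other study procedures.
- Reword the sentence that ties relatedness to rTMS so that it refers to either investigational device or to study participation, in line with the sentence before it.
- Under Collection and Recording, add the scanner and study procedures to the SAE attribution list.
- State that both AE/ADE and SAE/UADE collection cover the baseline MRI, and replace randomization with a starting point that exists in a single-group study, such as consent or the first study procedure.

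The cost is a wording amendment and a few form items. No visits, procedures or staff are added, and no sample-size or efficacy figure changes. Collecting events from baseline adds a short recording period for each participant.
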